11.3 Sponsor-Investigator Responsibilities

HCRN will send a SAE summary to the sponsor-investigator **within 1 business day** of receipt of SAE Submission Form from a site. The sponsor-investigator will promptly review the SAE summary and assess for expectedness and relatedness.

11.4 HCRN Responsibilities for Reporting SAEs to the FDA

11.4.1 Protocols Conducted Under an IND

HCRN has been designated to manage the Investigational New Drug Application (IND) associated with this protocol on behalf of the sponsor-investigator. HCRN will cross-reference this submission to Eli Lilly's and BMS's parent INDs at the time of submission. Additionally, HCRN will submit a copy of these documents to Eli Lilly and BMS at the time of submission to FDA.

HCRN will be responsible for all communication with the FDA in accordance with 21CFR312 which includes but is not limited to the 7- and 15-Day Reports, as well as an Annual Progress Report. Additionally, HCRN will submit a copy of these reports to Eli Lilly and BMS at the time of submission to FDA.

11.5 IND Safety Reports Unrelated to This Trial

Eli Lilly and Company and BMS will provide HCRN with IND safety reports from external studies that involve the study drugs to HCRN ([contact]) per their guidelines. HCRN will forward the safety reports to the sponsor-investigator who will review these reports and determine if revisions are needed to the protocol or consent. HCRN will forward these reports to participating sites **within 1 business day** of receiving the sponsor-investigator's review. Based on the sponsor-investigator's review, applicable changes will be made to the protocol and informed consent document (if required). All IND safety reports will also be made available to sites via the EDC system.

Upon receipt from HCRN, site investigators (or designees) are responsible for submitting these safety reports to their respective IRBs, as per their IRB policies.

12 STATISTICAL CONSIDERATIONS

12.1 Study Design

The primary objective of this study is to evaluate the response rate of checkpoint inhibitor with combination of the anti PD-1 agent, nivolumab and the anti VEGFR2 antibody, ramucirumab in subjects with previously-treated mesothelioma. The primary study endpoint is the response rate [complete response (CR) + partial response (PR)] of patients to this treatment. Nivolumab and ramucirumab will be given on Day 1 of each 14-day cycle. Treatment will continue up to 24 months (52 cycles) or until disease progression, unacceptable toxicity, subject refusal, or subject death. Subjects who voluntarily stop the study, have progressive disease, or unacceptable toxicities will be followed for a total of 24 months after initiation of study treatment.

Correlative research analyses include examining the relationship between best clinical response overall with tissue PD-L1, and at the end of Cycle 4 (Week 8) with changes in PD-L1 and cytokine genes expressions and number of CD8+ and Granzyme B+ T cells in tumor tissue from before therapy to the end of Cycle 4 (Week 8). Research analyses also include examining the relationship between changes in soluble PD-L1 level, during therapy (assessed pre-dose Cycles 1 and 5 [(Days 1 and 57 of treatment period, respectively)]) relative to baseline to the best clinical response (modified RECIST 1.1 criteria) and to treatment outcome.

12.2 Criteria for Stopping Study

The study will be stopped for safety reasons if ≥ 2 subjects in first 20 or ≥ 3 in first 30 subjects develop grade 5 therapy related toxicity during first 4 cycles of therapy.

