5.3.5 Dose Delay Due to Toxicity

If both drugs are held on Day 1 due to toxicity, the day treatment is resumed will be considered Day 1 of the cycle. If only one drug is held on Day 1 due to toxicity, the dose of that drug will not be made up.

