6.3.2 Nivolumab Dose Delay Criteria

Adverse events (both non-serious and serious) associated with nivolumab exposure may represent an immunologic etiology. These adverse events may occur shortly after the first dose or several months after the last dose of treatment. Nivolumab must be withheld for drug-related toxicities and severe or life-threatening AEs as per Table 3 below. See Section 5.4 for supportive care guidelines, including use of corticosteroids. **NOTE:** In addition to information in the table, permanently discontinue for any severe or Grade 3 drug-related AE that recurs or any life-threatening event. Subjects with intolerable or persistent Grade 2 drug-related AE may have study medication held at physician discretion. Permanently discontinue study drug for persistent Grade 2 adverse reactions for which treatment with study drug has been held, that do not recover to Grade 0-1 within 6 weeks of the last dose unless delay beyond 6 weeks allows for prolonged steroid taper to manage toxicity. In such cases, the Sponsor Investigator must be consulted prior to re-initiating treatment.

Table 3: Nivolumab dose modification guidelines for drug-related adverse events

Toxicity	Hold Treatment For	Timing for Restarting Treatment	Discontinue Subject
Diarrhea/Colitis	Grade 2-3	Toxicity resolves to Grade 0-1	Toxicity does not resolve within 6 weeks of last dose unless delay beyond 6 weeks allows for prolonged steroid taper to manage toxicity. In such cases, the Sponsor Investigator must be consulted prior to re-initiating treatment.
	Grade 4	Permanently discontinue	Permanently discontinue
Pneumonitis	Grade 2	Toxicity resolves to Grade 0-1	Toxicity does not resolve within 6 weeks of last dose unless delay beyond 6 weeks allows for prolonged steroid taper to manage toxicity. In such cases, the Sponsor Investigator must be consulted prior to re-initiating treatment.
	Grade 3-4	Permanently discontinue	Permanently discontinue
Hepatitis	≥ Grade 2 if subject has baseline AST, ALT or total bilirubin that is within normal limits; ≥ Grade 3 if subject has baseline AST, ALT or total bilirubin within the Grade 1 toxicity range	Toxicity resolves to Grade 0-1	Toxicity does not resolve within 6 weeks of last dose unless delay beyond 6 weeks allows for prolonged steroid taper to manage toxicity. In such cases, the Sponsor Investigator must be consulted prior to re-initiating treatment.

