11.2 Adverse Event (AE) Recording

- Adverse events (AEs) will be recorded from the time of consent until 100 days after treatment discontinuation of study drugs, or until a new anti-cancer treatment starts, whichever occurs first.
- AEs will be recorded regardless of whether or not the event(s) are considered related to the study drugs.
- All AEs will be recorded in the subject's medical record and on the appropriate study specific eCRF form within the EDC system.
- All AEs considered related to study drugs will be followed until resolution to \leq Grade 1 or baseline, deemed clinically insignificant, and/or until a new anti-cancer treatment starts, whichever occurs first.

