12.3 Sample Size

This is a non-randomized one arm study of nivolumab and ramucirumab. The primary study endpoint is the response rate [complete response (CR) + partial response (PR)] of patients for the therapy. Previous studies identified such response rate of 20% [Alley's Lancet Oncology paper 2017]. We hypothesize a response rate of 40%. Controlling for a probability of Type I error at 0.05 (one-sided), our sample size is estimated to be 33 to ensure 80% statistical power in successfully detecting an alternative response rate of 0.40, compared to a null rate of 0.2. With estimated up to 5% of patients that are not evaluable for primary endpoint, sample size will be increased to 35. Sample size analyses were conducted using the PASS software (NCSS, Kaysville, Utah, USA).

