13 TRIAL MANAGEMENT

13.1 Data and Safety Monitoring Board (DSMB)

This study will have a Data and Safety Monitoring Board (DSMB). The DSMB is chaired by an independent medical oncologist external to this trial. The DSMB will provide a recommendation to the sponsor-investigator after all information is reviewed. This information will also be provided to HCRN who will distribute to the site investigator/participating sites for submission to their respective IRB, according to the local IRB's policies and procedures.

The DSMB review will include but is not limited to:

- Adverse event summary report
- Audit results, if applicable
- Data related to stopping/decision rules described in study design
- Study accrual patterns
- Protocol deviations

The DSMB will review data a minimum of twice per year during the active study drug administration phase of the study.

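### The only pre-specified safety stopping rule does not count therapy-related deaths after cycle 4 or in subjects 31-35; those deaths are left to judgement with no numeric threshold

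*Combined protocol and SAP*

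**What the plan says.** Section 12.2 is one sentence. The thresholds for a safety stop are "≥ 2 subjects in first 20 or ≥ 3 in first 30 subjects". The only subjects who count towards them are those who "develop grade 5 therapy related toxicity during first 4 cycles of therapy". No operating characteristics are given, and no other section contains a numeric safety boundary for the trial.

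The surrounding text sets a wider frame:

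- **Exposure (12.1):** "Treatment will continue up to 24 months (52 cycles"), in 14-day cycles.
- **Enrolment (12.3):** "sample size will be increased to 35".
- **Timing of toxicity (6.3.2, on nivolumab):** "These adverse events may occur shortly after the first dose or several months after the last dose of treatment".
- **Safety collection (11.2):** adverse events are recorded "until 100 days after treatment discontinuation of study drugs", or until a new anti-cancer treatment starts if that is sooner. Section 11.3.1 uses the same window for serious events and also requires reporting of related serious events that come to light outside it.
- **Oversight (13.1):** "The DSMB will review data a minimum of twice per year" while study drug is being given. Its review covers an adverse event summary and the stopping-rule data, among other items, and leads to a recommendation to the sponsor-investigator.

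**The concern.** The rule and the safety collection are built on different views of when harm occurs. Collection follows each subject to 100 days past the last dose because late toxicity is foreseen. The rule looks only at the first four cycles. A therapy-related death in week 7 counts towards stopping, and one in week 10 does not, although both are collected and reported in the same way. The plan gives no reason for the difference.

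The boundary may therefore look more protective than it is. Someone who reads two in 20 or three in 30 will think of the regimen's overall rate of related death, whereas the rule responds only to the early part of that rate. Any share of deaths that falls later lowers the chance of stopping, and if all fall later the rule can never be met.

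**Working it through.** The plan states no stopping probability, so there is no figure to reproduce. The check computes what the written boundary does.

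**Inputs from the documents.** Thresholds: 2 in the first 20 or 3 in the first 30 (12.2). Window: 4 cycles of 14 days = 8 weeks. Maximum treatment: 52 cycles = 104 weeks (12.1). Planned subjects: 35 (12.3).

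**Inputs assumed.** The documents give neither a true rate of therapy-related death nor its timing. I use total rates of 2%, 5%, 10% and 15%, with 100%, 50% or 25% of those deaths inside the window.

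**Coverage.** 4/52 = 7.7% of maximum exposure. Subjects not covered: 35 − 30 = 5, and 5/35 = 14%.

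**Formula for the present rule.** Let p be the probability that a subject has a counted death, i.e. total rate × share inside the window. The study continues only if the first 20 subjects give 0 or 1 counted deaths and the first 30 give at most 2:

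P(stop) = 1 − P(X=0)·P(Y≤2) − P(X=1)·P(Y≤1), with X ~ Bin(20, p) and Y ~ Bin(10, p).

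**Worked case, p = 0.05.** P(X=0) = 0.3585, P(X=1) = 0.3774, P(Y≤2) = 0.9885, P(Y≤1) = 0.9139. So P(stop) = 1 − 0.3585 × 0.9885 − 0.3774 × 0.9139 = 1 − 0.3544 − 0.3449 = 0.301.

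**Formula for the amended count.** All related deaths count and the limit of three runs to subject 35. The expression is the same with Y ~ Bin(15, p) and p equal to the total rate. At p = 0.05, P(Y≤2) = 0.9638 and P(Y≤1) = 0.8290, so P(stop) = 1 − 0.3585 × 0.9638 − 0.3774 × 0.8290 = 0.342.

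**Probability of stopping**

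| Total related-death rate | Present rule, all in window | Present rule, half in window | Present rule, a quarter in window | All deaths counted, to subject 35 |
|---|---|---|---|---|
| 2% | 0.065 | 0.018 | 0.005 | 0.072 |
| 5% | 0.301 | 0.097 | 0.027 | 0.342 |
| 10% | 0.688 | 0.301 | 0.097 | 0.752 |
| 15% | 0.894 | 0.514 | 0.193 | 0.933 |

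If no related death falls in the window, the present rule gives 0 at every rate.

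**Which limit matters.** Take the half-late case.

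- Removing the time window while keeping 30 subjects gains 0.301 − 0.097 = 0.204 at 5%, 0.688 − 0.301 = 0.387 at 10%, and 0.894 − 0.514 = 0.380 at 15%.
- Extending from 30 to 35 subjects then adds 0.041, 0.064 and 0.039, about 4 to 6 points.

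The time window accounts for most of the loss.

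**The case against.** The strongest reply is that an early fixed window is a legitimate choice: it gives a quick, clearly attributable signal and leaves later events to people who can weigh them. The documents do provide for that. The DSMB reviews adverse events beyond the rule's own data (13.1). The sponsor-investigator receives each serious-event summary within one business day and assesses relatedness (Section 11, sponsor-investigator responsibilities). FDA 7- and 15-day reports apply (11.4.1). This stands, and it limits the point. A reader might infer that late deaths cannot stop the trial; the documents do not support that. They cannot trigger 12.2, but they can still lead to a stop by judgement.

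A reader might also infer that the protocol expects late immune-related deaths. It does not say so. Section 6.3.2 speaks of adverse events, serious and non-serious. The onset after many months described in 10.2.9 concerns endocrine events, mostly of low or moderate grade, and the fatal neurologic example there has no late timing attached.

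Three further arguments against the rule fail or weaken:

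- **Holds.** When both drugs are held, "the day treatment is resumed will be considered Day 1 of the cycle" (5.3.5). This lengthens the calendar window, so it captures more deaths, not fewer.
- **Semi-annual review.** Section 12.2 ties the stop to the count, not to a meeting date, and twice a year is a minimum.
- **Early toxicity with a later death.** Whether toxicity that begins in cycle 2 and proves fatal after treatment ends is counted depends on how the sentence is read. That is an ambiguity to settle, not a shown exclusion.

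One limit on the benefit also stands. The amended-count figures include every related death that eventually occurs. With about 24 months of enrolment, some would come after accrual has closed, when a stop protects only subjects still on treatment.

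**Conclusion.** The point holds in limited form. Section 12.2 is the only numeric safety boundary, and it disregards therapy-related deaths after cycle 4 and in subjects 31-35, although the protocol warns of late toxicity and already collects it. For those deaths the plan relies on discretion without a threshold.

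The size depends on timing that the documents do not give. If all related deaths are early, the time window costs nothing and only the small subject limit remains. If half are late, the chance of stopping at a true 10% rate is 30%, against 69% for the same thresholds over 30 subjects without the window and 75% with all 35 subjects counted. These figures assume independent subjects, a common rate and correct attribution of each death.

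**What to change.** Amend 12.2. Keep both thresholds and the present attribution wording. Count Grade 5 therapy-related toxicity from first dose through the existing 100-day safety window, in every treated subject, and carry the limit of three through subject 35. State that toxicity starting in the window and later proving fatal is counted, so that two readers would classify the same death alike. If the sponsor prefers the early window, 12.2 should say why later deaths are excluded.

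The change is one paragraph and needs no new data, because these deaths are already reported.

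The cost is in false stops and should be priced on the same timing assumption as the benefit. At a true total rate of 2%, the amended rule stops 7.2% of the time. The present rule stops 6.5% if all deaths are early, 1.8% if half are late and 0.5% if three quarters are late. The increase is therefore 0.7, 5.4 or 6.7 points. The sponsor should publish these operating characteristics with the amended rule. Broadening attribution to any possibly related death would add further false stops that these figures do not cover, so it is not proposed here.

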12.3 Sample Size

This is a non-randomized one arm study of nivolumab and ramucirumab. The primary study endpoint is the response rate [complete response (CR) + partial response (PR)] of patients for the therapy. Previous studies identified such response rate of 20% [Alley's Lancet Oncology paper 2017]. We hypothesize a response rate of 40%. Controlling for a probability of Type I error at 0.05 (one-sided), our sample size is estimated to be 33 to ensure 80% statistical power in successfully detecting an alternative response rate of 0.40, compared to a null rate of 0.2. With estimated up to 5% of patients that are not evaluable for primary endpoint, sample size will be increased to 35. Sample size analyses were conducted using the PASS software (NCSS, Kaysville, Utah, USA).

12.4 Analysis of Primary Objectives/Aims

The primary endpoint is determination of the response rate [complete response (CR) + partial response (PR)] with the combination of the anti PD-1 agent, nivolumab and the anti VEGFR2 antibody, ramucirumab in subjects with previously-treated mesothelioma; it will be calculated with associated 95% confidence interval using.

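### No planned output for the response rate matches the design's one-sided 0.05: Section 12.4 gives only a 95% confidence interval, whose lower tail is 2.5%

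*Combined protocol and SAP*

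**What the plan says.** Section 12.3 (Sample Size), repeated in the synopsis, sets the error rate and sidedness: "Controlling for a probability of Type I error at 0.05 (one-sided), our sample size is estimated to be 33". The benchmark is a 20% response rate ("compared to a null rate of 0.2"), the alternative is 40%, and the target power is 80%. Enrolment is raised to 35 to allow for up to 5% non-evaluable subjects.

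Section 12.4 (Analysis of Primary Objectives/Aims) is the only analysis text for the primary endpoint. It defines the response rate as CR plus PR and says "it will be calculated with associated 95% confidence interval using". As the text stands, the sentence ends there, with no interval method. Neither section gives a named test, a critical number of responders, a 90% interval, a one-sided limit, or a statement that the interval is descriptive. Section 12.5 uses the same 95% level for adverse-event proportions and for PFS and OS rates.

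**The concern.** A one-sided test at 0.05 corresponds to a one-sided 95% lower limit, which is the lower end of a two-sided 90% interval. A two-sided 95% interval puts only 2.5% in its lower tail. Since it is the only planned output, readers will set it against the 20% benchmark. The same data could then meet the error rate in Section 12.3 and still be reported with an interval that includes 20%. The affected count sits at the success boundary. With no stated rule, either reading could be adopted after the data are seen.

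**Working it through.** **Inputs.** All come from Section 12.3: null rate p0 = 0.20, alternative p1 = 0.40, one-sided alpha 0.05, power 0.80, 33 evaluable, 35 enrolled. The 95% level comes from Section 12.4. Assumptions of this review are that the 95% interval is two-sided and, where no other method is named below, that test and interval are exact binomial (Clopper-Pearson).

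**Step 1: the plan's own sample size.**
- Normal approximation: n = [1.645·√(0.2·0.8) + 0.842·√(0.4·0.6)]² / 0.2² = 28.6.
- With continuity correction: (28.6/4)·[1 + √(1 + 2/(28.6·0.2))]² = 33.4.
- Arcsine: 31.6.
- Exact binomial: 35 is the smallest n with alpha at most 0.05 and power at least 0.80.

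The stated 33 is within two subjects of the last three. Inflation gives 33/0.95 = 34.7, so 35 is reproduced. The allowance itself leaves 34 or 35 evaluable, because one of 35 is 2.9% while two of 35 is 5.7%.

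**Step 2: the boundary result at 35.** For 12/35 (34.3%), P(X ≥ 12 | 35, 0.20) = 0.034, which meets one-sided 0.05. The exact 90% interval is 21.1% to 49.6% and excludes 20%. The 95% interval depends on the method:

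| Method | 95% lower limit | 95% upper limit | Includes 20%? |
|---|---|---|---|
| Clopper-Pearson | 19.1% | 52.2% | yes |
| Wald | 18.6% | 50.0% | yes |
| Wilson | 20.8% | 50.9% | no |
| Agresti-Coull | 20.8% | 50.9% | no |
| Jeffreys | 20.3% | 50.8% | no |

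**Step 3: smallest count whose exact lower limit exceeds 20%.** For a rule of r or more responders, alpha = P(X ≥ r | n, 0.20) and power = P(X ≥ r | n, 0.40).

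| n | 90% interval: r, alpha, power | 95% interval: r, alpha, power |
|---|---|---|
| 33 | 12, 0.022, 72.4% | 12, 0.022, 72.4% |
| 34 | 12, 0.027, 76.7% | 13, 0.011, 64.6% |
| 35 | 12, 0.034, 80.5% | 13, 0.014, 69.4% |

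At 34 and 35 the two levels differ by one responder. At 33 they agree.

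**Step 4: how often it would matter.** P(X = 12 | 35, 0.40) = 11.1% and P(X = 12 | 35, 0.20) = 2.0%. For 12/34 at a true rate of 40% it is 12.1%.

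**Step 5: test and interval must use one method.** At 11/33, z = (11 − 6.6)/√(33·0.2·0.8) = 1.91, or 1.70 with continuity correction. Both exceed 1.645, so a z test rejects. The exact tail probability is 0.0508 and the exact 90% lower limit is 19.95%, so the exact method does not reject. Changing the level to 90% without naming the test would leave this disagreement in place.

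**The case against.** The strongest reply is that Section 12.4 describes estimation. It never says the interval is compared with 20% or decides success. Section 12.5 uses 95% throughout, so 95% may simply be the document's reporting level, and pairing a one-sided 0.05 design with a descriptive 95% interval is common in phase II. This stands. A reader might infer that the plan tests 20% at one-sided 0.025, or that the trial really has 69.4% power. The documents do not support either inference: the 69.4% arises only if someone uses the exact 95% lower limit as the success rule, which the plan does not say.

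It is also fair that three of the five interval methods show no conflict at 12/35, and that at the design's own 33 evaluable the exact method loses nothing. Both limit the size of the point. They do not remove it, because the plan names no method and 34 or 35 evaluable subjects is within its own allowance. Wilson also avoids the conflict at 12/35 only when paired with an exact test. Paired with its own uncorrected z test, the boundary moves to 11/35 (z = 1.69), where the Wilson 95% interval is 18.6% to 48.0% and includes 20%. That pairing has a true alpha of 0.075, so it is no way out.

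Finally, once a cut-off is prespecified, the cut-off decides and the 95% interval becomes descriptive. That is right, and it is why the fix below states the test as well as the interval level. No cut-off is stated now.

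**Conclusion.** The point holds in a limited form and is minor. The design's error rate is one-sided 0.05, and the plan contains no test or interval that matches it; the one planned interval, read conventionally, corresponds to 0.025 in the lower tail. A 95% interval is not an error in itself. If it were read against 20% with the exact method, one more responder would be needed at 34 or 35 evaluable (13 instead of 12), and power would be 64.6% against 76.7%, or 69.4% against 80.5%. At 33 there is no difference. The ambiguity touches one response count per sample size, with about an 11% chance at 35 if the true rate is 40%.

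This rests on reading the unqualified interval as two-sided and, for the power figures, on Clopper-Pearson limits. If the unfinished sentence was meant to name another method, the stated level would still be 95%, but whether 12/35 conflicts could change, as the table of methods shows.

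**What to change.** In Section 12.4, state that the comparison with 20% uses the exact binomial test at one-sided 0.05, reported with the matching Clopper-Pearson two-sided 90% interval (equivalently, the one-sided 95% lower limit), and that the 95% interval is descriptive. Name the method for both intervals, which also completes the unfinished sentence. Under this wording, 12 responders are needed at 33, 34 or 35 evaluable, and test and interval agree.

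The cost is one or two sentences and two intervals in the report, each of which must be labelled with its level and role. No extra subjects or data are needed. The change does not raise power at 33 or 34 evaluable, which stays at 72.4% and 76.7% under the exact rule; that is a separate matter.
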